11.4.4 Interim analyses

After the treatment of 50 participants and again after 200 participants, the independent Data and Safety Monitoring Board (DSMB, including external clinical experts as well as patient and public representatives) will meet to discuss summary statistics about safety outcomes (see section 10 *SAFETY*). In addition, the adherence to treatment will be assessed in these interim analyses. If the proportion of non-adherence is above 10% (i.e., more than 10% of participants received fewer than 7 of the planned 10 doses), the study team will assess the reasons why doses were missed and implement actions (e.g., additional training) to increase adherence.

11.4.5 Safety analysis

The following adverse events and safety outcomes will be analysed descriptively by study group:

- Serious adverse reactions or serious adverse events in the 90 days following study entry
- The following adverse events of special interest until 14 days after study entry during the index hospital stay:
 - Clinical signs compatible with serotonin syndrome
 - Laboratory signs of haematotoxicity
- Acute kidney injury defined using modified Kidney Disease Improving Global Outcomes (KDIGO) criteria, modified according to SNAP trial:
 - Increase in serum creatinine by 26.5 µmol/l or more at any time from baseline entry to day 5

OR

- Increase in serum creatinine by 1.5 times or more the level at study entry (baseline) within 14 days of study entry
- *Clostridioides difficile*-associated diarrhoea

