5.4 Safety Outcomes

Safety outcomes encompass any serious adverse events (SAE) and serious adverse reactions (SAR) until day 90 as well as adverse events of special interest. Definitions can be found in chapter 10.1.1 *Definition and assessment of (serious) adverse events and other safety related events*.

Adverse events of special interest

(details on how they are assessed is provided in chapter 9.2.4.1 *Adverse events*:

- Clinical signs of serotonin toxicity until day 7
- Laboratory signs of myelosuppression until day 7
- Hyperlactatemia until day 7
- Acute kidney injury
- *C. difficile*-associated diarrhoea within 90 days

Further information on safety outcomes (mortality, SAR, AEs leading to discontinuation of trial intervention) can be found in chapters 5.1 *Primary Outcome* and 5.2 *Secondary Outcomes*.

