³ Choose the result that represents the highest level recorded between day 6-14.

⁴ Linezolid trough concentration is only measured in a subset of participants in participating centres.

⁵ Adverse events of special interest until day 7 include: serotonin toxicity, myelosuppression, hyperlactataemia; until day 14: acute kidney injury; until day 90: C. difficile-associated diarrhoea.

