9.3.6 Assessment of routine laboratory measurements (day 1-7)

Laboratory assessments at start and during treatment will be part of the clinical routine. Either on the day before or on the day of study treatment start, participants will receive routine blood sampling which includes blood count (Hb, Tc, Lc), measurement of renal function (creatinine) and liver function (ALT, gGT), as well as inflammatory parameter (CRP). The study team will review the blood samples at start and during treatment and will re-order any missing laboratory measurements from the collected blood samples if, in rare cases, the necessary measurements for the study according to the visit plan were not routinely performed. No additional blood should be drawn to assess clinical routine measurements. The blood count should be measured 4 times between day 1 (-1) and day 7 (± 1), creatinine and CRP at least on day 1 and day 5 (± 1), creatinine also on day 14 (± 3) if a participant is still hospitalised.

9.3.7 Subproject *Molecular mechanisms of S. aureus bacteraemia* (day 1 until 48h after the patient's first negative blood culture)

Only for a subgroup of patients included in Basel, Switzerland.

Blood will be used to determine the location of *S. aureus* in the blood (intra- or extracellular).

For this, a maximum of one additional 7.5 ml EDTA tube of blood per day will be collected from day 1 until follow-up blood cultures remain negative for 48 hours.

- For patients who consented to further analysis of *S. aureus* in their blood, blood samples will be collected daily. If no routine blood work is performed on an eligible day, an additional blood draw should be performed to collect the sample.
- For patients enrolled via the confirmation of an independent physician under emergency exception from informed consent requirements, blood samples will only be collected during routine blood drawing.
- For patients who refused consent to further analysis in the blood, no additional blood samples for the subproject will be taken.

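### The safety analysis uses a 14-day window for two events that are collected only to day 7, and leaves out hyperlactataemia

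*Protocol*

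**What the plan says.** Section 11.4.5 sets out a descriptive safety analysis by study group. One entry is headed "The following adverse events of special interest until 14 days after study entry during the index hospital stay" and has two items under it: "Clinical signs compatible with serotonin syndrome" and "Laboratory signs of haematotoxicity". The other entries are serious adverse events and reactions over 90 days, acute kidney injury with its own day-5 and 14-day limits, and C. difficile-associated diarrhoea with no window stated. Hyperlactataemia does not appear.

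The outcome definitions in 5.4 read differently: "Clinical signs of serotonin toxicity until day 7", "Laboratory signs of myelosuppression until day 7" and "Hyperlactatemia until day 7". Footnote 5 to the schedule in 9.1 agrees: "Adverse events of special interest until day 7 include: serotonin toxicity, myelosuppression, hyperlactataemia". The same footnote reserves day 14 for acute kidney injury and day 90 for C. difficile-associated diarrhoea. Section 9.3.6 fixes the blood sampling: "The blood count should be measured 4 times between day 1 (-1) and day 7", with a tolerance of one day on the last count.

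**The concern.** The analysis section states a window, and that window is twice as long as the one over which the two events are defined and collected. If 11.4.5 is followed as written, days 8 to 14 enter the table with no scheduled blood count and no scheduled serotonin assessment behind them. The reader of the results would see a 14-day rate. In fact it would be a day-7 rate plus incidental findings, and those could come only from participants who were still inpatients.

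Hyperlactataemia has a definition, a window and a testing rule, but no line in the analysis. Section 3.7 describes it as rare but potentially severe, so a by-arm count is something readers of the safety results will look for.

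**Working it through.** The plan gives no figure to reproduce, and no sample size or alpha is involved. The check sets the windows and the event lists side by side. It takes serotonin syndrome in 11.4.5 to be the same event as serotonin toxicity elsewhere, and haematotoxicity to be the same as myelosuppression.

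**Windows**

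| Event | 5.4 | 9.1, footnote 5 | 9.2.4.1 | 9.3.11, bullets | 11.4.5 |
|---|---|---|---|---|---|
| Serotonin toxicity | day 7 | day 7 | day 7 | day 7 | day 14, index stay |
| Myelosuppression | day 7 | day 7 | day 7 | day 7 | day 14, index stay |
| Hyperlactataemia | day 7 | day 7 | day 7 | day 7 | not listed |
| Acute kidney injury | none stated | day 14 | day 5 and day 14 limbs | creatinine at day 5 and day 14 | day 5 and day 14 limbs |
| C. difficile diarrhoea | 90 days | day 90 | 90 days | 90 days | none stated |

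For the first two rows, four places agree on day 7 and 11.4.5 alone says day 14. The restriction to the index hospital stay is also absent from the definitions in 5.4.

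**Is anything planned between day 8 and day 14?**

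- Blood counts: 9.3.6 asks for four, ending at day 7 (±1). This matches the four marks in the 9.1 schedule. The tolerance can carry the last count to day 8 but no further.
- Serotonin assessment: the 9.1 row for these events ends at day 7.
- Creatinine does continue to day 14, but it serves acute kidney injury.
- Other capture: 10.1 collects all serious adverse events, and otherwise the predefined events of special interest as the protocol outlines them. That outline ends at day 7. A non-serious cytopenia on day 10 has no planned capture, yet it lies inside the 11.4.5 window.

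**Does 9.3.11 support day 14?** Its heading gives day 1-5, day 14 ±3 and discharge day. Its own bullets give day 7 for serotonin toxicity, myelosuppression and hyperlactataemia. The day-14 visit is used there for creatinine and for the C. difficile review. The heading is a further inconsistency, since it names no day 7 at all, and it does not supply a day-14 assessment for these events.

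**Event list.** Section 5.4 names five events of special interest. Section 11.4.5 covers four: serotonin, haematological, kidney and C. difficile. Hyperlactataemia is the one missing. A serious case would still be counted among the serious events to day 90; a non-serious case would appear nowhere in 11.4.5.

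**Size.** An estimate would need event rates and the proportion still in hospital for days 8 to 14. The protocol gives neither, so no figure is offered.

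**The case against.** The strongest reply is that little harm follows. The analysis is descriptive, the trial is blinded and placebo-controlled, and the collection rules are the same in both arms. Within the index stay, participants are seen daily and have regular blood sampling (9.3.11, 9.3.12), so many day 8-14 events would be noticed anyway. Serious events are collected and reported to day 90. Section 11.4.1 also calls the listed analyses current intentions and promises a detailed analysis plan, which could add hyperlactataemia.

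Much of this stands, and it limits the point. It does not remove it. Routine care in hospital is not scheduled ascertainment, and it ends at discharge. Equal collection rules also do not guarantee equal time under observation. Section 11.2 assumes that linezolid shortens hospital stay; if it does, linezolid participants would be observed for less of days 8 to 14. Whether that happens is unknown. As for the later plan, 11.4.5 does not leave the matter open: it fixes a window that conflicts with the definitions. Section 11.4.6 then requires every departure from the protocol's analysis to be listed and justified.

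Three stronger readings are tempting, and the documents do not support them.

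- A reader might infer that the reported rates will be wrong. Counts to day 7 are unaffected. What is shown is a mislabelled window with incomplete ascertainment after day 7.
- A reader might apply the 1-3% incidence of hyperlactataemia in 3.7 to the linezolid arm to predict how many cases would be lost. Section 3.7 says that the incidence is not well reported, takes the figure from retrospective studies, and expects few such events with five days of treatment. Lactate is also measured only on clinical suspicion (9.2.4.1).
- A reader might count adverse events leading to study drug discontinuation as a further omission from 11.4.5. They are part of the DOOR complication component (5.1) and a named secondary outcome (5.2), and 5.4 sends the reader there.

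**Conclusion.** The inconsistency is real and stands in the current text. Section 11.4.5 sets a 14-day, index-stay window for two events that the rest of the protocol defines and collects to day 7, and it omits one of the five prespecified events of special interest. Followed as written, it yields an incompletely ascertained rate under a 14-day label, and no by-arm result for non-serious hyperlactataemia.

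The consequence is confined to the descriptive safety tables. The primary analysis, alpha and power are untouched. The conclusion rests on reading the differently named serotonin and haematological events as the same events, and on the schedule and 9.3.6 being the whole of the planned collection for them. The point deserves correction because the safety tables should match the data behind them, and the correction costs very little.

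**What to change.** In 11.4.5:

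- Report serotonin toxicity, myelosuppression and hyperlactataemia over the day-7 window in which they are collected, using the same event names as 5.4.
- Leave the acute kidney injury definition unchanged, with its separate day-5 and day-14 limbs. Shortening it to a single day-14 window would blur the two.
- State the 90-day window for C. difficile-associated diarrhoea.

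In 9.3.11, reconcile the heading with the bullets beneath it.

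The cost is a few lines of wording and one extra table row. No new data collection is needed if day 7 is kept. It is best done before the safety reviews after 50 and 200 participants (11.4.4), so that those summaries use the same windows as the final report.

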9. STUDY ASSESSMENTS

9.1 Study flow chart/ table of study procedures and assessments

Study Schedule

	Screening	Enrolment	Intervention phase					In-Hospital Follow-Up (applicable only if participant remains hospitalised)				Close-out
Time point	0-72h before randomisation		Day 1	Day 2	Day 3	Day 4	Day 5	Day 7	Day 14	Day 28	Discharge day	Day 90
S. aureus positive blood culture	X											
Identification of patient		X										
Eligibility checks		X										
Informed consent		X										
Randomisation			X									
IMP administration			X	X	X	X	X					
Time point	0-72h before randomisation		Day 1 (-1 day)	Day 2	Day 3 (±1 day)	Day 4	Day 5 (±1 day)	Day 7 (±1 day)	Day 14 (±3 days)	Day 28 (±4 days)	Discharge day	Day 90 (±7 days)
Clinical assessments												
Baseline data			X ¹									
SIRS criteria								X				
All-cause mortality								Assessed until day 90				
Clinical failure										X	X	X
Length of hospital stay											X	
Length of ICU stay											X	
Antibiotic and/or surgical treatment												X
Laboratory assessments												
Blood cultures				X			X ²					
Creatinine			X				X			X ³		
CRP			X				X					
ALT and gGT			X				X			X ³		
Blood count (Hb, Tc, Lc)			X		X		X	X				
Linezolid trough conc.							X ⁴					
Microbiological failure										X	X	X
New antibiotic resistance												X
Patient reported outcomes												
Quality of life (SF-36)												X
Return to usual level of function												X
Safety assessments												
Serotonin toxicity, myelosuppression, hyperlactataemia ⁵			X	X	X	X	X	X				
Acute kidney injury ⁵							X		X			
C. difficile-associated diarrhoea ⁵												X
SAE / SAR			Collected until day 90									

Abbreviations: S. aureus – *Staphylococcus aureus*; SAE – Severe Adverse Event; SAR – Severe Adverse Reaction; SIRS - Systemic Inflammatory Response Syndrome; ICU – Intensive Care Unit; CRP – C-Reactive Protein; ALT – Alanine Transaminase; gGT – Gamma-glutamyl Transferase; Hb – Haemoglobin; Tc – Thrombocytes; Lc – Leukocytes; SF-36 – Short Form-36

¹ Baseline data include: date of hospital admission, index blood culture, linezolid susceptibility, ethnicity, vital signs, comorbidities, standard antibiotic treatment, markers of severity (mechanical ventilation, cardiac arrest, use of vasopressors, ICU), injection drug use, mental health diagnosis.

² Assessment of persistent bacteraemia. Only required if day 2 blood culture is positive or recorded if done as part of standard of care.

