Acute kidney injury according to the modified Kidney Disease Improving Global Outcomes (KDIGO) stage 1 is defined as an increase in serum creatinine of $\geq 26.5 \mu\text{mol/L}$ from randomisation (baseline) to study day 5 or an increase in serum creatinine by 1.5 times or more the level of randomisation within 14 days of

randomisation. To collect this outcome, the serum creatinine at baseline (on randomisation day 1 or the calendar day prior to randomisation), day 5 (± 1 day), and only if participant remains hospitalised, at day 14 (± 3 days) will be documented in the eCRF. The values will be captured from available data in the hospital information system or from the participant's primary care physician, respectively.

- *C. difficile*-associated diarrhoea within 90 days.

The treating clinicians will assess for *C. difficile* infection based on the centre-specific diagnostic algorithm if clinical suspicion arises due to diarrhoea during antibiotic treatment. *C. difficile* infection will be evaluated on day 14, at discharge, and on day 90 by reviewing the participant's electronic health records. If a participant reports severe diarrhoea during a 90-day follow-up phone call, occurring after discharge and managed outside the centre, the responsible physician may be contacted to determine if a *C. difficile* infection was diagnosed.

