- We modelled hospital length of stay using a log-normal model with any of the complications listed in the definition above as an independent variable; the parameters for this model were derived from the retrospective USB data, and the expected 20% relative reduction in hospital length of stay due to the intervention was applied to the mean of the log-transformed data when generating synthetic datasets.
- Missing data were accounted for in the simulations (i.e., 10% for worse level of function and only 3% for all other components as these data will be available from routinely collected data). In case of missing DOOR components, the comparison among participants was made with the following DOOR domain.

Under the assumptions listed above, 550 participants are required to show a significant effect of the intervention. Since it is possible that some patients themselves or their next of kin withdraw consent post-randomisation, we increased the target sample size by 10% to minimise the risk of being underpowered. Hence, we plan to include 606 participants (303 participants in each study arm).

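### Late acute kidney injury is sought mainly in participants still in hospital, a stay that linezolid is expected to shorten; this modestly favours linezolid in the descriptive safety comparison

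*Protocol*

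**What the plan says.** **Kidney injury, definition.** Section 11.4.5 of the protocol has two limbs. One is an absolute creatinine rise of 26.5 µmol/l or more up to day 5. The other is "Increase in serum creatinine by 1.5 times or more the level at study entry (baseline) within 14 days of study entry". This bullet carries no restriction to the hospital stay.

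**Kidney injury, data.** Section 9.2.4.1 collects baseline and day-5 creatinine and, "only if participant remains hospitalised, at day 14 (± 3 days) will be documented in the eCRF". Sections 9.3.6 and 9.3.11 repeat the inpatient condition. The schedule in 9.1 heads its later in-hospital columns "In-Hospital Follow-Up (applicable only if participant remains hospitalised", and its creatinine footnote reads "Choose the result that represents the highest level recorded between day 6-14". Section 9.2.4.1 then adds "The values will be captured from available data in the hospital information system or from the" participant's primary care physician. Section 9.3.11 names only the hospital information system.

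**Haematotoxicity and serotonin syndrome.** Section 11.4.5 groups these two under "The following adverse events of special interest until 14 days after study entry during the index hospital stay". Sections 5.4, 9.1 (footnote 5), 9.2.4.1 and 9.3.11 run both to day 7, and 9.3.6 plans the last blood count at day 7 (±1).

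**Length of stay.** The sample size in 11.2 builds in "the expected 20% relative reduction in hospital length of stay due to the intervention". Stay is also the fourth component of the primary outcome.

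**Analysis.** Section 11.4.5 says that these outcomes are analysed descriptively by study group.

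**The concern.** The 1.5-fold limb of kidney injury is defined over 14 days for everyone. The late creatinine values that could show it come mainly from people who have not yet gone home, and time to discharge is something the treatment is expected to change. If linezolid shortens the stay as planned, its participants are observed for less of days 6 to 14. A given late risk then yields fewer detected events in that arm.

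Section 3.9 lists kidney injury among the notable adverse events of linezolid, and 5.4 makes it an event of special interest. The direction of the error favours linezolid, and its size grows with the drug's success on length of stay. The collection of serious events to day 90, by telephone after discharge (9.3.12), does not fill the gap, because a creatinine rise can be a silent laboratory finding.

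**Working it through.** The protocol gives no kidney-injury rate, event timing or length-of-stay distribution, so there is no figure of its own to reproduce. The only relevant input is the 20% shorter stay in 11.2. Everything else below is assumed and shown as a range.

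**Step 1. In-hospital time on days 6 to 14.** Let the stay L be log-normal with median m and log-SD s.

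- P(L > t) = 1 − Φ((ln t − ln m)/s)
- Expected in-hospital days between day 5 and day 14 = ∫ from 5 to 14 of P(L > t) dt
- Linezolid median = 0.80 × control median

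| Control median, log-SD | In hospital at day 14, control / linezolid | In-hospital days in window, control / linezolid | Ratio of days |
|---|---|---|---|
| 12, 0.6 | 0.399 / 0.265 | 5.91 / 4.75 | 0.80 |
| 16, 0.8 | 0.566 / 0.455 | 6.70 / 5.88 | 0.88 |
| 20, 0.8 | 0.672 / 0.566 | 7.39 / 6.70 | 0.91 |
| 25, 0.6 | 0.833 / 0.724 | 8.42 / 7.92 | 0.94 |

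Over the grid of medians 12 to 25 days and log-SD 0.6 to 1.0, the ratio of in-hospital days is 0.80 to 0.94. The share still in hospital at day 14 is 8 to 15 percentage points lower on linezolid. Because the schedule takes the highest value from days 6 to 14, the ratio of days is the fairer measure.

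**Step 2. Effect on the whole 14-day comparison.** Suppose equal true risk, a fraction f of events after day 5, full observation to day 5, and late events seen only while in hospital. With c the mean probability of still being in hospital over days 6 to 14:

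observed risk ratio = (1 − f + f × c_linezolid) / (1 − f + f × c_control)

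Take f = 0.2 to 0.4, control median 10 to 22 days and log-SD 0.6 to 1.0.

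- Largest shift (median 10, log-SD 0.6, f = 0.4): (0.6 + 0.4 × 0.387) / (0.6 + 0.4 × 0.520) = 0.755 / 0.808 = 0.93
- Smallest shift (median 22, log-SD 1.0, f = 0.2): (0.8 + 0.2 × 0.719) / (0.8 + 0.2 × 0.787) = 0.944 / 0.957 = 0.99

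A true ratio of 1 would therefore appear as 0.93 to 0.99, a shift of about 1 to 7%.

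**Step 3. In events.** Extra events missed on linezolid = 303 × risk × f × (c_control − c_linezolid), with true risk assumed at 10 to 20%.

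- Low: 303 × 0.10 × 0.2 × (0.75 − 0.65) = 0.6
- High: 303 × 0.20 × 0.4 × (0.57 − 0.46) = 2.7

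That is about 1 to 3 events.

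**Step 4. Sensitivity to the reading of 20%.** Section 11.2 says that the reduction was applied to the mean of the log-transformed stays. Taken literally (log-mean × 0.80), a median of 12 days becomes 12^0.8 = 7.3. The ratio of in-hospital days on the Step 1 grid is then 0.56 to 0.76, and the whole-window ratio on the Step 2 grid is 0.86 to 0.96.

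**The case against.** Several stronger readings are tempting, and the protocol does not support them.

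- A reader might infer that the restriction to the index hospital stay in 11.4.5 covers kidney injury. As printed, it heads only serotonin syndrome and haematotoxicity. The kidney restriction comes from 9.2.4.1, 9.3.6 and 9.3.11, and the primary-care sentence in 9.2.4.1 softens it.
- A reader might extend the argument to late haematological harm. No blood count is scheduled after day 7 (±1) in either arm, so the main defect there is the conflict between the day-7 and day-14 windows.
- A reader might infer that discharged participants will be counted as event-free, or that raw counts will hide late harm. Section 11.4.5 says only that the analysis is descriptive. Denominators are ordinary analysis-plan content, and 11.4.1 promises such a plan. A rise on day 8 before discharge on day 12 would also be captured under the schedule's footnote.
- A reader might multiply a true 1.2-fold excess by the ratio still in hospital at day 14 and obtain 1.2 × 0.664 = 0.80 to 1.2 × 0.889 = 1.07. That applies only to events visible solely at day 14. It leaves out the limb to day 5 and anything seen on days 6 to 13.

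Serious events are collected to day 90, dosing ends on day 5, and 8.2.1 calls earlier discharge unlikely.

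An inpatient denominator is not a clean remedy either. If late kidney injury itself keeps people in hospital and true counts are equal, dividing by those still in hospital creates a false linezolid excess of 1/0.889 = 1.12 to 1/0.664 = 1.51.

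These points reduce the size and narrow the scope. They leave standing that the protocol itself fixes a mainly inpatient source for a 14-day outcome, and is inconsistent on post-discharge values.

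**Conclusion.** The point holds for acute kidney injury and is modest. Detection on days 6 to 14 depends on a stay that the trial expects linezolid to shorten. In-hospital time in that window would be about 0.80 to 0.94 of control, and the comparison over the whole window would shift by about 1 to 7% in linezolid's favour.

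This rests on assumed log-normal stays, a 20% shorter median, 20 to 40% of events after day 5, deaths ignored, no primary-care values, and late risk unrelated to stay. If early discharges are at lower risk, the shift is smaller. If the log-mean reading of 11.2 is meant, it is larger (4 to 14%). Kidney injury up to day 5 is little affected.

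For haematotoxicity, the finding is the day-7 versus day-14 contradiction, which must be reconciled.

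**What to change.** In 11.4.5 or the analysis plan:

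- Report kidney injury up to day 5 separately, as the comparison least affected by length of stay.
- For days 6 to 14, show by arm the number with a creatinine value and the number without one, with discharge and death as reasons.
- State that an absent value after discharge is not treated as no event.
- Present any rate among inpatients, or per in-hospital day, only as a labelled sensitivity display, because it conditions on a post-randomisation outcome.

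In the protocol text:

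- Reconcile 9.2.4.1 with 9.3.6 and 9.3.11 on whether post-discharge creatinine values are captured, with one rule applied identically in both arms.
- Reconcile the haematotoxicity and serotonin windows in 11.4.5 with those in 5.4, 9.1, 9.2.4.1 and 9.3.11.

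The cost is a few sentences and one extra safety table. The table uses laboratory values and discharge and death dates that are already collected.
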